# 12.5 Non-English Speaking Participants

Almost all Liberians speak Liberian English, which is the language used for the standard consenting procedure. In the event that a potential participant does not understand Liberian English, the study team will attempt to identify a non-family member to provide verbal translation of the consent form and will only use a family member to provide the translation if a

non-family member is not available. As way of background, this was rarely required on the PREVAIL protocols. This practice follows Liberian norms.

#### 13.0 DATA AND SAFETY MONITORING

Data gathered during this study will be monitored by the principal investigator for safety and compliance with protocol-specified requirements.

The principal investigator will meet monthly with the lead associate investigators to review summary statistics for participants enrolled, and safety and compliance with protocol-specified requirements, including study-related adverse events. Site visits will be performed during cataract surgery campaigns. If any study-related adverse events occur, they will be reported according to requirements of the local and NIH IRBs.

# 13.1 Criteria for Stopping the Study

Preliminary post-operative data will be reviewed after 30 cases once available by the principal investigator and lead associate investigators. An improvement in visual acuity is expected from cataract surgery. Therefore, the study will be stopped early if participants on average appear to experience loss of vision. Additionally, transmission of Ebola or death will result in pausing the study until further review by the NIH IRB and Liberian Ethics Committee.

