In the first year of presentation, approximately 1 in 10 survivors and close contacts presented with cataract (unpublished data). Such cataracts may be due directly to either intraocular inflammation or long-term steroid use, often needed to address the severe panuveitis present in disease, but may

also develop naturally. Cataract surgery is cost-effective and clearly indicated to help vision, but without knowledge of whether viral persistence exists, it is not known what infection control practices are necessary for surgery to be performed safely.

A similar proportion of patients have developed post-inflammatory epiretinal membrane (which requires more complex vitreoretinal surgery to address). Therefore, a need exists for the long-term development of surgical capacity in addition to short-term knowledge regarding intraocular persistence of virus. Although the mainstay of EVD treatment is largely medical, it is clear that a significant proportion of ophthalmic sequelae will require surgical intervention.

For survivors who are blind, cataract surgery is necessary to restore visual function, allowing re-integration into society, and for personal safety, to avoid falls and collisions. However, surgical outcomes among Ebola survivors are unknown. Ebola-associated ocular comorbidities such as hypotony must be accounted for post surgically. Given that cataracts associated with the rubella virus are characterized by severe postoperative inflammation due to viral persistence within the lens, requiring aggressive postoperative anti-inflammatory treatment with steroids, we must monitor intraocular inflammation in the postoperative period. Intraocular surgery among young individuals is also often marked by a robust inflammatory response. Both factors may influence outcomes in Ebola-associated cataract. We propose the study of surgical outcomes that will inform care in other affected countries and for future Ebola-affected patients.

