## 1.2 Rationale

At present, the safety and optimal execution of cataract surgery in Ebola survivors is unknown. Specifically, it is unknown whether survivors experience extended periods of inflammation post-operatively and require adjusted management guidelines, and whether Ebola virus persists in the anterior chamber and lens, requiring special precautions by the surgical team. Currently, the pathophysiology of viral persistence in the eye is not understood.

Analysis of anterior chamber fluid and lens material will help answer these unknowns, as will close surgical follow-up management and monitoring. Since lenticular tissue is normally disposed of during cataract surgery, the collection and analyses of this material will provide a unique opportunity to assess a potential location for virus in Ebola-affected eyes, to further elucidate the pathophysiology underlying viral persistence. Following EVD survivors during the post-surgical

period will allow us to evaluate surgical outcomes and the effect of post-surgical comorbidities in this population, which are currently unknown.

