#### 3.0 PARTICIPANTS

This study involves recruiting EVD survivors and controls who have a clinical need for cataract surgery, which will be performed using the small incision cataract surgery technique which is standard practice in Liberia. Therefore, we will enroll all individuals who meet study eligibility criteria and would otherwise be eligible (clinically) to undergo cataract surgery.

The accrual ceiling is 120 people, with up to 60 EVD survivors and up to 60 controls. Current estimates of numbers of survivors and controls meeting eligibility criteria is lower, at about 35-45 survivors and 35 controls.

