## 4.0 STUDY DESIGN AND METHODS

This is a prospective, natural history study to evaluate the persistence of Ebola viral RNA in the eyes of Ebola survivors and assess the response to cataract surgery in survivors as compared to controls. For the purposes of the study procedures and analysis, EVD survivors and controls who are seropositive are considered cases with potential for persistence of Ebola viral RNA and will have an initial aqueous humor tap to assess for the presence of Ebola viral RNA by GeneXpert. All EVD survivors, defined as those who are seropositive for the Ebola virus, testing negative for Ebola viral RNA and control subjects will undergo clinically indicated cataract surgery. Subjects will be evaluated 1 day, 1 week, 1 month, and 3, 6, 9, and 12 months after surgery for inflammation, safety and visual outcome assessments, and more often as clinically indicated. Participant enrollment and all study visits, including cataract surgery, will be performed at various sites in Liberia.

**Co-enrollment guidelines:** Participants may be co-enrolled in the PREVAIL III Natural History Study and may be co-enrolled in other studies; however, study staff should be notified of co-enrollment on any other study.

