# Cataract surgery visit

All survivors who have tested negative for Ebola viral RNA in the aqueous humor, as well as controls, will proceed with cataract surgery within 30 days of the screening visit. It is expected that most if not all surgeries will take place the second week of the protocol. If the surgery does not occur within 30 days of the screening visit, the screening visit procedures will be repeated prior to surgery. For Ebola survivors, the aqueous humor tap must be performed within three months of cataract surgery. If cataract surgery has been delayed beyond the three-month window following the aqueous tap, then the surgery can no longer be performed under this protocol as the resources to perform the AC taps on Ebola survivors are available in country for only a limited period of time.

For control participants, aqueous fluid sampling will be performed during the cataract surgery and will be used in the GeneXpert verification.

Cataract surgery will be performed by qualified eye surgeons with formal cataract surgery training. The surgeons may be AI's on the protocol (i.e. [name]) or other qualified available eye surgeons with appropriate credentials at ELWA hospital. Surgeries will be performed at the ELWA hospital. Anesthesia for the surgery will consist of peribulbar block. Routine manual small incision cataract surgery, with use of biometry to assess for an appropriate intraocular lens to be implanted, will be performed for all participants. All subjects will receive standard postoperative topical

antibiotic and anti-inflammatory regimens. During surgery, the individual lens components (capsule, nucleus, and cortex), which would normally be discarded, will be placed into neutral-buffered formalin for immunohistochemistry for detection of Ebola virus protein.

Immediately after surgery, participants will be asked to rest in beds provided by ELWA and will stay overnight. It is expected that participants will be fully ambulatory the day after surgery. They will then receive their travel allowance to commute home. Those from distant locations will stay at ELWA through the Week 1 postoperative exam.

If a participant is having any medical problems or difficulty with ambulation after the surgery, they will be cared for at ELWA until they are able to safely travel home. If needed for complications with their eye, participants will be able to access medical care and be reimbursed for their commuting expenses.

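### Section 13.1 stops for vision only on a pooled average, so a minority of survivor eyes could lose vision without meeting the rule

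*Combined protocol and SAP*

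**What the plan says.** Section 13.1 is the only place in the protocol that sets study-level stopping criteria. It has three parts:

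- One scheduled look: "Preliminary post-operative data will be reviewed after 30 cases once available", carried out by the principal investigator and lead associate investigators.
- One stopping criterion: "the study will be stopped early if participants on average appear to experience loss of vision". No visit, acuity measure, size of loss or group is given.
- One pause criterion: "transmission of Ebola or death will result in pausing the study until further review by the NIH IRB and Liberian Ethics Committee".

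The neighbouring sections add monitoring but no thresholds. Section 7.0 provides for adverse event monitoring at visits, and 7.1 covers withdrawal of individuals. Section 13.0 sets a monthly investigator review of safety, with reporting of study-related adverse events to the IRBs. Section 15.0 refers reportable events to the IRB under a named policy.

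Three other parts of the protocol bear on the rule. Section 3.1.1 admits eyes with corrected acuity worse than 20/40 where cataract is the main cause, so there is room to gain. Section 1.2 calls the safety of surgery in survivors unknown and adds that "it is unknown whether survivors experience extended periods of inflammation post-operatively". Section 3.0 expects "about 35-45 survivors and 35 controls".

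**The concern.** An average is a poor detector of harm to a few. When most operated eyes are expected to improve, their gains offset the losses of a minority. Harm from infection, retinal detachment or uncontrolled inflammation would take that form: severe in some eyes, absent in the rest. Section 6.0 acknowledges that surgical complications can end in worse vision or blindness.

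Pooling adds to the problem. Survivors are the group in whom safety is unknown, yet the rule refers to participants as a whole, so improvement in controls can cover losses in survivors. If only the written rule is applied, a cluster of harmed survivor eyes would not meet it. Any action would then rest on the investigators' judgement at the monthly and 30-case reviews and on IRB reporting.

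**Working it through.** The plan states no operating characteristic for its stopping rule, so there is no figure to reproduce. The check asks how many eyes must lose vision before the average turns negative.

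**Inputs.** From the documents: 30 cases (13.1); 35-45 survivors and 35 controls expected (3.0). Assumed, because the documents give none: each unharmed eye gains *g* = 0.3 to 1.0 logMAR, each harmed eye loses *l* = 0.2 to 2.0 logMAR, and each eye has one fixed value. The average is read as the mean change in logMAR.

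**Step 1: threshold.** With *k* of *n* eyes harmed, the mean is a loss when *k·l* > (*n* − *k*)·*g*, that is, when *k/n* > *g*/(*g* + *l*).

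- Lowest in the range: *g* = 0.3, *l* = 2.0 gives 0.3/2.3 = 13%; 30 × 0.13 = 3.9, so *k* = 4 of 30.
- Highest: *g* = 1.0, *l* = 0.2 gives 1.0/1.2 = 83%; 30 × 0.83 = 25.0, which must be exceeded, so *k* = 26 of 30.

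**Step 2: chance that the rule is met if 20% of eyes truly lose vision.** This is P(Binomial(30, 0.2) ≥ *k*).

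| Loss *l* | *g* = 0.3 | 0.4 | 0.6 | 0.8 | 1.0 |
|---|---|---|---|---|---|
| 2.0 | *k* = 4: 88% | 6: 57% | 7: 39% | 9: 13% | 11: 2.6% |
| 1.0 | *k* = 7: 39% | 9: 13% | 12: 0.9% | 14: 0.1% | 16: <0.1% |

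For losses of 0.6 or less the largest value is 2.6% (*g* = 0.3, *l* = 0.6, *k* = 11). The rule responds mainly when losses are very large relative to gains.

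**Step 3: effect of pooling.** If 30 operated participants follow the expected mix, survivors number between 30 × 35/70 = 15 and 30 × 45/80 = 16.9, so about 15 to 17. This ignores survivors who test PCR positive or are seronegative. Take *g* = 0.4 and *l* = 1.0, with no control losing vision.

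- Pooled: 30 × 0.4/1.4 = 8.6, so 9 survivor eyes must lose vision.
- Survivors alone: 15 × 0.4/1.4 = 4.3 and 17 × 0.4/1.4 = 4.9, so 5 eyes.

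Pooling therefore nearly doubles the number of survivor eyes needed under these assumptions.

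**Step 4: a count as the alternative.** The event is a seropositive survivor eye that has lost vision or had a serious complication, each eye counted once. The probability of reaching the count is:

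| Rule | True rate 5% | 10% | 20% | 30% |
|---|---|---|---|---|
| 6 or more of 30 | 0.3% | 7% | 57% | 92% |
| 3 or more of 15 | 4% | 18% | 60% | 87% |
| 3 or more of 17 | 5% | 24% | 69% | 92% |

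The true rates are assumptions; the documents give no background rate.

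**The case against.** The strongest case against is that protection is already substantial. Adverse events are reviewed monthly, the 30-case look covers post-operative data generally, and events go to the IRBs. Participants have a round-the-clock telephone contact (6.0), referral for persistent inflammation (4.3) and complication care for up to two years (4.4). The surgery is clinically indicated, and for such surgery a criterion based on average benefit is a defensible choice. All of this stands, and it is why the point is minor. It does not remove the gap, because none of these arrangements says what finding should halt surgery, and section 16.0 says survivors' access to surgery is limited by lack of safety data.

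A pause also has a cost. Under the cataract surgery visit in 4.3, a survivor whose surgery falls more than three months after the aqueous tap can no longer be operated on under the protocol. A pause could therefore cost someone the operation after an invasive procedure. This stands and shapes the fix. So does the limit on benefit: "It is expected that most if not all surgeries will take place the second week of the protocol", in which case much of the exposure comes before any review.

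The magnitude depends on assumed gains and losses, and trigger probabilities run from under 0.1% to 88%. That is also right. The figures illustrate the mechanism; they do not measure the risk in this trial.

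Four stronger readings are tempting and are not supported:

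- *That the plan lacks safety monitoring.* It does not; what is missing is an action level.
- *That inflammation needs its own stopping trigger.* Cell grade is a primary outcome under study, and section 1.1 notes that "Intraocular surgery among young individuals is also often marked by a robust inflammatory response". Leaving it out of the rule is reasonable.
- *That the 30-case look means 30 seropositive participants.* Section 4.0 does say that "EVD survivors and controls who are seropositive are considered cases with potential for persistence of Ebola viral RNA", but 13.1 concerns post-operative data and then speaks of participants, so 30 operated participants is the natural reading.
- *That there is no data and safety monitoring board.* The front-page checkbox cannot be read in the available text. Section 13 names only investigators as reviewers, which does not settle it.

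**Conclusion.** The point holds in a limited form. The stated vision criterion is a pooled average in eyes selected to improve, and no other section supplies a study-level action level for a count of harmed eyes. A minority of survivor eyes could lose vision without the criterion being met. Under the assumed range, between 4 and 26 of 30 eyes must lose vision before it is. That an average can hide a harmed minority does not depend on the particular values chosen; the size does. It also rests on reading the criterion as mean change in acuity and on one fixed gain or loss per eye.

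This is a minor, cheap improvement to safety wording. It does not call the trial's validity or its primary analyses into question.

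**What to change.** 1. **Tabulate by group.** At the 30-case review and the monthly reviews, report separately for seropositive survivors and controls the number of operated eyes with acuity worse than at screening, with exact 95% intervals. Compare like with like: presenting or pinhole vision before month 1, best-corrected acuity from month 1, as Appendix 1 schedules them. Show serious complications and cell grade alongside.

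2. **Add a survivor-specific count.** The pooled average should no longer be the sole vision criterion. A single pre-set number of seropositive survivor eyes that have either lost vision or had a serious complication should prompt review by the NIH IRB and Liberian Ethics Committee. It must be one combined count, not a pause on any one event: at an assumed complication rate of 1% to 3%, one event in 30 eyes would occur with probability 1 − 0.99^30 = 26% to 1 − 0.97^30 = 60%. Fix the number, the denominator it applies to, the minimum loss and the visit with both committees before the first surgery. The counts of 6 in 30 and 3 in 15-17 are examples.

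3. **Expedite review for survivors already tapped**, so that a pause does not carry them past the three-month limit.

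No inflammation trigger is proposed.

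**Cost:** protocol wording and one table from data already scheduled. The downside is a chance of an unneeded pause: at background rates of 5% to 10%, 0.3% to 7% for 6 of 30, 4% to 18% for 3 of 15, and 5% to 24% for 3 of 17. If most surgeries fall in the second week, the gain is mainly for later accrual within the one-year period.

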## 14.0 QUALITY ASSURANCE

The Principal Investigator will oversee the quality assurance process in this study with assistance from the Liberian Principal Investigator, [name], Adjunct Principal Investigator, [name], and the following Associate Investigators: Drs. [name], and [name]. Monitors will perform QA review at random intervals and will communicate directly with the principal investigator.

## 15.0 REPORTABLE EVENTS

Reportable events will be tracked and submitted to the IRB as outlined in Policy 801.

#### 16.0 ALTERNATIVE THERAPIES

The alternative to participation is to either not pursue cataract surgery at this time or to pursue cataract surgery outside of the study.

For control participants, this would be standard of care surgery which would be arranged through normal mechanisms in Liberia. Access to cataract surgery is variable in Liberia and depends on geography and means. The public hospital in Monrovia, which treats all patients free of charge, does not currently have the capacity to perform cataract surgery. Surgery is available privately in Monrovia to those with means to pay for it. There are also some free surgical outreach efforts which are performed by a cataract surgeon in regions outside of Monrovia, on a schedule determined by the surgeon.

For Ebola survivors, the ability to get surgery is currently limited by the lack of available safety data. At the completion of this study, additional safety data should be available to better inform standard of care management of Ebola-associated cataracts.

## 17.0 PRIVACY

All research activities will be conducted in as private a setting as possible.

# 18.0 CONFIDENTIALITY

Samples and data will be stored using codes assigned by PREVAIL data operations. Data will be kept in in password-protected computers. Samples will be kept in locked storage. Only study investigators will have access to the samples and data.

#### 19.0 CONFLICT OF INTEREST

The NIH guidelines were distributed to all the investigators. There are no conflicts-of-interest to report for NIH investigators. Non-NIH investigators will abide by the conflict-of-interest policies of their own institutions.

#### 20.0 TECHNOLOGY TRANSFER

No technology transfer agreement is in place for this protocol.

# 21.0 COMPENSATION

An allowance for transportation will assist with travel to the proposed surgical site and to the sites of follow-up study and clinical care visits. There will be no penalty for failure to complete the protocol. The allowance values will be consistent with those used throughout the PREVAIL III

study. The allowance will consist of \$20 US for the information session, consenting, screening and for all visits to ELWA Hospital and \$10 US for all visits at JFK Hospital. Participants will also receive a \$10 US allowance for transportation for clinical care visits which may take place at any designated clinical care site for this study.

Participants will receive compensation for all study visits per standard PREVAIL procedure, where they collect the allowance at JFK for visits at JFK (in the amount of \$10 US) and collect the allowance at ELWA for visits at ELWA (in the amount of \$20 US, which is increased in amount since ELWA is a further transportation distance for most of the participants). In addition, participants will receive free of charge housing and food when they are at the ELWA location overnight, such as the night before and after cataract surgery. In addition, participants will receive a travel allowance (in the amount of \$10 US) for any additional clinical eye examinations that are required for optimal healing.

Participants from distant locations will be transported to Monrovia free of charge for all visits which require them to be in Monrovia, including for consent, screening, procedures to include aqueous tap and surgery, and certain post-operative visits. Participants from distant locations will be provided transportation, accommodations, and food during the period of time when they must stay in Monrovia to receive consent, examinations including history and physical and screening, surgery, and certain post-operative visits. Local participants from Monrovia will be asked to present the night before surgery and will be provided accommodations and food so that they will be available for surgery the next day. All participants will spend the night after surgery at accommodations provided by the study so that they are available for the postoperative day one visit. Food will be provided whenever participants receive accommodations as part of this study.

# **APPENDIX 2: STUDY UNDERSTANDING EVALUATION FORM**

Subject I.D. #:	Subject Initials: Protocol Title:
	ent regarding item 1 below. Ask the patient questions to use in asking the questions in order to help the patient with total score of 6.
ITEMS:	SCORE
1. Is the patient alert and able to communic 0= no	ate with examiner? 1= yes
2. Ask the patient to describe the purpose of 0= not able to describe or doesn't answer	of the study 1= able to describe
3. Ask the patient to name at least two (2) p study.  0 = not able to list or doesn't answer	otential risks incurred as a result of participation in the $1 = \text{able to list two risks}$
4. Ask the patient to name at least two (2) the study.  0 = not able to list expectations, or doesn't	things that will be expected of him/her to do while in answer $1 = $ able to list two expectations
5. Ask the patient to explain what he/she we any longer. 0 = doesn't know or doesn't answer,	ould do if he/she decides not to participate in the study  1 = talk to any staff member
6. Ask the patient to explain what he/she wo 0 = doesn't know, or doesn't answer	ould do if he/she is experiencing distress or discomfort.  1 = talk to any staff member
	TOTAL

SIGNATURES I hereby certify that the answers to items 2-6	the above patient is alert, able to communi above.	cate and able to give acceptable
Rater Initials	Rater Signature	Date
Witness		Date
